### **21.3. Independent Data Monitoring Committee**

The trial will be presented for review to the ETOP IDMC at each of their meetings which take place 4 times a year. Accrual and safety will be monitored.

### **21.4. Publication**

The results of the trial will be published according to the ETOP publication policy (appendix 3).

### **21.5. Clinical trial insurance**

ETOP will contract the appropriate liability insurance for this trial. Patients who suffer injuries due to the trial should report them immediately to their physician. The local group/institution should report all alleged claims immediately to the ETOP Coordinating Office.

## **21.6. Quality assurance**

ETOP conducts trials according to the ICH Good Clinical Practice (GCP) guidelines. The Trial Data Manager reviews each eCRF as it is received. In addition, the ETOP Medical Reviewer reviews each case at specific timepoints. ETOP conducts periodic audit visits to ensure proper trial conduct, verify compliance with GCP, and perform source data verification.

The Investigator should ensure that source documents are made available to appropriately qualified personnel from ETOP or its designees, or to ethics committee and health authority inspectors after appropriate notification.

At regular intervals during the clinical trial, the Centre will be contacted, through monitoring visits, letters or telephone calls, by a representative of the Monitoring Team to review study progress, investigator and patient compliance with clinical trial protocol requirements and any emergent problems. These monitoring visits will include but not be limited to review of the following aspects: patient informed consent, patient recruitment and follow-up, SAE documentation and reporting, AEs with pre-specified monitoring documentation and reporting, AE documentation, dispensing IMP, compliance with protocol, drug accountability, concomitant therapy use, quality of data and storage of blood and serum samples.

## **21.7. Protocol adherence**

Investigators ascertain that they will apply due diligence to avoid protocol deviations. Under no circumstances should the investigator contact ETOP or personnel monitoring the trial to request approval of a protocol deviation, as no deviations are permitted. The investigator should document and explain any deviations from the approved protocol. The investigator should promptly report any deviations to the Sponsor and to the EC concerned in accordance with the applicable EC policies and procedures. If the investigator feels a protocol deviation would improve the conduct of the trial this must be considered a protocol amendment, and unless such an amendment is developed and activated by the sponsor and approved by the IRB/IEC/ERB it cannot be implemented. All protocol deviations will be recorded.

## **21.8. Data protection**

The samples and data collected will be coded to protect patient confidentiality. Each patient will have a unique identifier assigned by the RDE facility ETOPdata. Sites are responsible to keep a patient log locally in order to be able to link the unique identifier to the record of the patient.

Biological material will be assigned the same unique identifier. No identifiable / personal data will be stored in the trial database or the tissue repositories in the central labs.

Biological material will be transferred outside the treating institution for central screening and review. Results of the assays will be coded only by the patient identifier.

Regulatory authorities and pertinent Ethics Committees (IRB/ERB) may have access to patient data on-site. ETOP audit or monitoring personnel will also have access to such data on-site.

## 21.9. Record retention

The centre must retain all essential documents according to ICH GCP. This includes copies of the patient trial records, which are considered as source data, patient informed consent statement, laboratory printouts, drug inventory and destruction logs, and all other information collected during the trial. These documents are to be stored until at least 15 years after the termination of the trial. ETOP guarantees access and availability of the data entered into ETOPdata for at least 15 years after the termination of the trial.

Longer retention may be required for participating centres according to national regulations.

In the event that the Principal Investigator retires or changes employment, custody of the records may be transferred to another competent person who will accept responsibility for those records. Written notice of such transfer has to be given to ETOP and the local Ethics Committee at least 1 month in advance.

- **4. Additional secondary analysis:** accrual and baseline characteristics, treatment administration and follow-up, secondary and exploratory analysis
- 5. Technical issues: data retrieval, testing, handling of missing data, reporting conventions

Trial oversight (as per protocol version 2.0, Amendement1; AM1)

STIMUI is a randomized open-label phase II international multicentre clinical trial aiming to demonstrate superiority of consolidation with nivolumab and ipilimumab versus observation after chemo-radiotherapy and prophylactic cranial irradiation (PCI), in patients with radically treated limited-stage small cell lung cancer (SCLC).

SCHEMA 1. Trial design under protocol AM1

STIMULI is a trial with block stratified randomization balanced by institution. After completion of the 4 cycles of chemotherapy, thoracic radiotherapy and PCI, patients who have not progressed can be randomized to one of the two treatment arms. The two stratification factors are: number of fractions of radiotherapy (twice-daily vs once-daily) and positron emission tomography—computed tomography (PET-CT) (done vs not done)

1.1 Objectives and Endpoints

Primary objective

According to protocol AM1, the **primary objective** of the study is to evaluate if patients treated with chemo-radiotherapy and PCI followed by consolidation treatment (nivolumab plus ipilimumab) have a better outcome in terms of progression-free survival (PFS) and overall survival (OS) compared to patients treated with chemo-radiotherapy and prophylactic cranial irradiation without consolidation treatment.

Co-primary endpoints:

- Progression-free survival (PFS) according to RECIST 1.1 criteria based on the local radiologist assessment
- Overall survival (OS)

Important notes:

- Following a subsequent modification in trial design, without requiring protocol amendment, PFS alone was set to be the primary endpoint of the trial, with OS becoming a secondary endpoint. This is further described in section 1.4.2.
- PFS (measured from randomization) are compared between treatment arms only for randomized patients.
- Patients randomized to ipilimumab monotherapy before the protocol AM1, i.e., under the original protocol version, will be excluded from the present final efficacy analysis, and will be evaluated separately.

Secondary endpoints:

- Objective response determined by RECIST 1.1 criteria
- Time to treatment failure (TTF)
- Adverse events graded according to CTCAE v4.0

Exploratory endpoints:

- Time to treatment discontinuation (TTD)
- Duration of response (DoR)

Details on the calculation of endpoints are provided in section 2.2.

1.2 Most important eligibility criteria

Inclusion criteria at enrolment:

- Histologically or cytologically confirmed small cell lung carcinoma
- Untreated (with the exception of 1 cycle of chemotherapy given prior to enrolment) limited stage disease (LD) as defined by stage I-IIIB based on 7th TNM classification (IASLC classification for SCLC proposal). M0 proven by
 - Whole body FDG-PET CT including a contrast-enhanced CT of thorax and upper abdomen (incl. liver, kidney, adrenals); OR contrast-enhanced CT of thorax and upper abdomen (incl. liver, kidney, adrenals) and bone scan; AND
 - Brain MRI (or contrast enhanced CT of the brain).
 Within 28 days before start of chemotherapy
- Age ≥18 years
- ECOG performance status 0-1
- Adequate hematological, renal, hepatic and liver function
- Pulmonary function FEV1 of 1.0L or >40% predicted value and DL_{CO} >40% predicted value

Exclusion criteria at enrolment:

- Patients with mixed small-cell and non-small-cell histologic features
- Patients with pleural or pericardial effusions proven to be malignant
- Documented history of severe autoimmune or immune mediated symptomatic disease that required prolonged (>2 months) systemic immunosuppressive treatment (e.g. steroids) such as ulcerative colitis and Crohn's disease, rheumatoid arthritis, systemic progressive sclerosis (scleroderma), systemic lupus erythematosus, or autoimmune vasculitis (eg, Wegener's granulomatosis)
- Patients with an autoimmune paraneoplastic syndrome requiring concurrent immunosuppressive treatment
- Interstitial lung disease or pulmonary fibrosis
- Women who are pregnant or in the period of lactation
- Patients with any concurrent anticancer systemic therapy (except for chemotherapy cycle
 1)
- HIV, Hepatitis B or Hepatitis C infection
- Patients who have had in the past 5 years any previous or concomitant malignancy EXCEPT adequately treated basal or squamous cell carcinoma of the skin, in situ carcinoma of the cervix or bladder, in situ ductal carcinoma of the breast
- Previous radiotherapy to the thorax (prior to inclusion)
- Planned mean lung dose >20 Gy or V20 >35%

Inclusion criteria at randomization:

- Chemo-radiotherapy completed per protocol: 4 cycles of chemotherapy, 85% of PTV of thoracic radiotherapy, as well as completed, mandatory PCI
- Non-PD after chemo-radiotherapy and PCI

1.3 Trial treatment

After enrolment, the patient will receive or, if included after the first chemotherapy cycle, continue receiving standard of care treatment for limited disease SCLC consisting of chemoradiotherapy and PCI.

- Chemotherapy: will be started in the week following enrolment (alternatively, maximum 1 cycle of chemotherapy may be administered before enrolment), and consists of a total of 4 cycles of cisplatin (25 mg/m2 i.v. on days 1 3 or 75 mg/ m2 on day 1) or carboplatin (AUC 5-6, calculated according Calvert formula, i.v. on day 1), plus etoposide (100 mg/ m2 i.v. days 1 3), repeated every 3 weeks (+/- 3 days without cycle delay).
- Concomitant Thoracic Radiotherapy: Accelerated twice-daily administration of 45 Gy in 30 twice-daily fractions of 1.5 Gy (6-8 hours apart), 5 days per week for 3 weeks, or an allowed, but not-recommended schedule of 56 Gy, given in 28 once-daily fractions of 2 Gy, 5 days per week for 6 weeks. Two options are allowed: Thoracic radiotherapy MUST start either from day 1 of cycle 1 or day 1 of cycle 2. Radiotherapy start at day 1 of cycle 3 is allowed if patient is enrolled after the first cycle only but should be exceptional. Optimally, radiotherapy should start at the latest on day 1 of cycle 2.
- PCI: 25 Gy in 10 fractions starting between day 8 and day 15 of chemotherapy cycle 4 and finished not later than day 29 from start of cycle 4.

After_randomization, which should take place within 5-6 weeks after day 1 of cycle 4 (between days 35 and 42 of cycle 4)

Experimental arm

Induction phase:

To start within 6-8 weeks (42-56 days) after the start of chemotherapy cycle 4, and not more than 2 weeks (14 days) after the date of randomization.

- Nivolumab at a dose of 1 mg/kg i.v. over a period of 30 minutes,
 followed (on the same day) by
- Ipilimumab at a dose of 3 mg/kg i.v. over a period of 90 minutes, once every 3 weeks (+/3 days, without dosing delay), 4 cycles

Maintenance phase:

To start 3 weeks (21 days) after the last Investigational Medical Product (IMP) dose of induction phase.

Nivolumab 240 mg i.v. over a period of 30 minutes, once every 2 weeks (+/- 2 days, without dosing delay), for a maximum of 12 months from start of maintenance phase.

Observation arm

No further treatment.

1.4 Statistical design, sample size and power

1.4.1 Based on protocol AM1

This is a 1:1 randomized phase II trial (stratified by twice-daily vs once-daily radiotherapy and PET-CT done vs not done) with co-primary endpoints PFS and OS. The **overall one-sided significance level of 0.05** is split to 0.**01 for PFS** and 0.**04 for OS**. A total of 325 patients are expected to be enrolled in 36 months of accrual time, leading to **260 patients randomized** to the two arms based on a 20% attrition rate due mainly to early progression events during the first 4 months after enrolment. An additional 3% loss to follow-up is assumed during the trial after randomization. A trial duration of 87 months is necessary for the **required 212 deaths** to be observed, while the main analysis of PFS will be performed when **148 PFS events** have occurred, which is expected at approximately 45 months. Using the log-rank test, the achieved power is 80% for PFS at the 45-months evaluation and 78% for OS at the end of the trial.

Median PFS and OS for the observation arm are expected to be 13.1 and 20.7 months, as measured of randomization. Taking into account that the patients randomized are of better prognosis than the total patients enrolled, the expected increase in medians for the cohort of patients in the experimental arm is 9.7 months and 9 months for PFS and OS respectively. This translated to a PFS HR of 0.57 and OS HR of 0.70.

The trial will end when either the total number of 212 deaths has been observed or at a maximum of 7.5 years from the first patient enrolment date.

Calculations are performed using the EAST package and simulations were run in the R statistical package.

1.4.2 Modifications after premature accrual closure

Because of the low accrual rate as well as additional strategic considerations unrelated to the scientific rational of the trial design, trial's funding source (Bristol-Myers Squibb, BMS) informed ETOP on 18 March 2019 that cannot continue funding the STIMULI trial. Therefore, the Trial Steering Committee decided to close the accrual into the trial prematurely as of 30 April 2019. Note that no safety concerns led to the decision of accrual closing.

Patients who already consented were still allowed to be enrolled until 30 April 2019. After this date, no new patients would be allowed to be enrolled into the trial. Treatment and follow-up for

all included patients continued as per protocol. Patients in the chemoradiotherapy phase who meet the criteria, would be still allowed to be randomized.

Thus, taking into account the reduced number of randomized patients and the corresponding initially required events (148 PFS events, 212 OS events) which were not possible to be observed anymore, the statistical design was modified.

According to this latest statistical modification, the primary endpoint of the trial is now defined as only the PFS (previous: co-primary PFS and OS) using the overall one-sided significance level of 0.05 (previous: 0.04 for PFS and 0.01 for OS). The hypotheses for PFS remain the same (PFS HR=0.57, with 13.1 months median PFS assumed in the observation arm versus 22.8 in the experimental). In this setting, the number of the required PFS events, for testing the PFS hypothesis with 80% power, at 5% significance level, is 81 (in: 148 events).

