### **Statistical considerations:**

Hyperfractionated accelerated radiotherapy has been shown to be more efficacious than radiotherapy given in a long overall treatment time. By giving twice-daily fractionation (BID), late reacting normal tissues are spared compared to the tumour, with as a consequence more temporarily acute oesophagitis.

The value of twice daily (BID) radiotherapy given early and concurrently to chemotherapy was examined in landmark trials and in a meta-analysis which will be our benchmark data. After a median follow-up of over 8 years, 2-year overall survival (OS) for BID and QD radiotherapy, respectively, were 47% and 41%. Assuming that half of included patients will receive BID and QD respectively, the median OS is therefore expected to be 20.7 months in the observation. Median progression-free survival (PFS) is expected to be 13.1 months.

PFS and OS will be evaluated as co-primary endpoints. Hazard ratios of 0.70 for OS and 0.57 for PFS are to be detected with adequate power. The overall one-sided significance level of 0.05 for the logrank test is divided into 0.04 for OS and 0.01 for PFS.

A trial duration of 7.5 years from enrolment of the first patient is necessary for the required 212 deaths to be observed. The main analysis of PFS will be performed when 148 PFS events have occurred, which is expected at approximately 45 months. The achieved power is 78%

for OS at the end of the study, and 80% for PFS at 45 months. A total number of 260 patients is required to be randomised.

It is expected that after the chemo-radiotherapy phase, about 20% of treated patients will have progressed or will not receive PCI and can therefore not be randomised. Thus, approximately 325 patients will be enrolled in order to randomise 260 patients under amendment 1, at an estimated accrual time of 3 years.

**Total trial duration: 7.5 years** from enrolment of the first patient

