### **18.3. Co-primary endpoint: OS and PFS**

OS and PFS will be measured from randomisation and compared between treatment arms only in the cohort randomised under amendment 1.

The 2-year survival rate for the observation arm is estimated to be approximately 44% (47% for BID and 41% for QD radiotherapy, assuming half of included patients will receive BID and QD respectively). Median PFS and OS are expected to be 13.1 and 20.7 months.

For the experimental arm, medians as measured from randomisation are assumed to be 29.7 and 22.8 months for OS and PFS respectively (OS HR=0.70; PFS HR=0.57), taking into account that the patients randomised are of better prognosis than the total patients enrolled.

The overall one-sided significance level of 0.05 is split to 0.04 for OS and 0.01 for PFS. A total of 325 patients are expected to be enrolled in 36 months of accrual time, leading to 260 patients randomised to two arms based on a 20% attrition rate due mainly to early progression events during the first 4 months after enrolment. An additional 3% loss to follow-up is assumed during the trial after randomisation.

A trial duration of 87 months is necessary for the required 212 deaths to be observed, while on the main analysis of PFS will be performed when 148 PFS events have occurred, which is

expected at approximately 45 months. Using the log-rank test, the achieved power is 78% for OS at the end of the trial, and 80% for PFS at the 45-months evaluation.

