### **Total trial duration: 7.5 years**

The trial will end when either the total number of 212 deaths has been observed or at a maximum of 7.5 years from the first patient enrolment date.

Alternative scenarios for the co-primary endpoint of PFS and OS were run each in 10,000 simulations. The overall one-sided alpha level of 0.05 was split to 0.04 for OS and 0.01 for PFS. The alternative hypothesis of treatment benefit corresponds to an HR for PFS equal to 0.55, 0.60 and 0.65 and an OS HR of 0.7. A piecewise exponential survival distribution was assumed based on the above assumptions, omitting the lower end of the distribution time, i.e., events occurring before randomisation. The follow-up after randomisation was simulated according to the alternative of interest.

Power of 78% for testing OS from randomisation to end of trial and of 80% for testing PFS were generally aimed and achieved for the different scenarios. The probability of rejecting the null hypothesis regarding OS given that the null hypothesis regarding PFS was rejected was of the order of 85%-87%, while at least one rejection was achieved (power for co-primary) from 88% to 91% of the time, with 67-68% observed joint rejection.

Calculations are performed using the EAST package and simulations were run in the R statistical package.

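### Do the reversed PFS/OS alpha split in SAP 1.4.2, and a superseded 148-event target that does not reproduce at 80% power, call for a change to the plan?

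*SAP*

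**What the plan says.** **Superseded design (amendment 1).** The protocol summary states: "The overall one-sided significance level of 0.05 for the logrank test is divided into 0.04 for OS and 0.01 for PFS". Protocol 18.3 repeats it: "The overall one-sided significance level of 0.05 is split to 0.04 for OS and 0.01 for PFS". The paragraph on simulated scenarios says it a third time: "The overall one-sided alpha level of 0.05 was split to 0.04 for OS and 0.01 for PFS". SAP 1.4.1 gives the same split. The PFS analysis was due at 148 events, expected at about 45 months, and OS needed 212 deaths. For power, Protocol 18.3 reports that "the achieved power is 78% for OS at the end of the trial, and 80% for PFS at the 45-months evaluation". The design hazard ratios were 0.57 for PFS (medians 13.1 and 22.8 months) and 0.70 for OS (20.7 and 29.7 months).

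**Current design.** After accrual closed early, SAP 1.4.2 makes PFS the only primary endpoint, "using the overall one-sided significance level of 0.05 (previous: 0.04 for PFS and 0.01 for OS". It keeps the PFS hypothesis and says the number of events needed for 80% power, "at 5% significance level, is 81 (in: 148 events". SAP 2.1 times the final analysis at 81 PFS events. SAP 3 repeats the one-sided 5% error, 80% power and 81 events, and names the stratified log-rank test as the formal comparison.

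**The concern.** SAP 1.1 records that OS was demoted without a protocol amendment and sends the reader to 1.4.2 for the explanation. A late change of primary endpoint in an open-label trial should be described correctly, and 1.4.2 misstates what it replaced. As printed, the one-sided alpha for PFS appears to rise 1.25-fold (0.04 to 0.05). It actually rose five-fold (0.01 to 0.05), because the share held for OS was released.

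The printed figures also do not explain the fall from 148 to 81 events. A reader who checks it finds that neither the printed split nor the true split gives that ratio, and that 148 events carry more than the stated 80% power at one-sided 0.01. If either slip reached the live decision rule, the trial could be tested at the wrong level or stopped at the wrong count. That is what has to be ruled out.

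**Working it through.** **Inputs.** 1:1 allocation (SAP 1.4.1); PFS hazard ratio 0.57, or 13.1/22.8 = 0.5746 from the medians; OS hazard ratio 0.70; 148 and 81 PFS events; 212 deaths.

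**Formulas.**
- Schoenfeld: events = 4(z_a + z_b)² / (ln HR)²; power = Φ(½√d·|ln HR| − z_a).
- Freedman: events = [(1+HR)/(1−HR)]²(z_a + z_b)².
- Normal quantiles: 1.645 (one-sided 0.05), 1.751 (0.04), 2.326 (0.01), 0.842 (80% power).

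**1. The current target.** At one-sided 0.05 and HR 0.5746: 4 × (1.645 + 0.842)² / 0.554² = 80.5, so 81. At HR 0.57 Schoenfeld gives 78.3. The power of 81 events is 80.2% (HR 0.5746) or 81.2% (HR 0.57) by Schoenfeld, and 78.4% or 79.4% by Freedman. The rule in force reproduces.

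**2. Which split is right?**

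| Test | one-sided 0.01 | one-sided 0.04 | stated power |
|---|---|---|---|
| PFS, 148 events, HR 0.57–0.5746 | 83–86% | 94–95% | 80% |
| OS, 212 deaths, HR 0.70 | 60–61% | 79–80% | 78% |

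(Ranges cover Schoenfeld and Freedman.) The stated OS power fits only 0.04, and the stated PFS power is far closer to 0.01. The arithmetic agrees with the protocol and SAP 1.4.1, so the bracket in SAP 1.4.2 is the one that is transposed.

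**3. The step from 148 to 81.** At fixed hazard ratio and 80% power, the event requirement scales with (z_a + z_b)².
- 0.01 to 0.05: ratio (3.168/2.486)² = 1.62, a fall of 38% (131 to 81).
- 0.04 to 0.05: ratio (2.592/2.486)² = 1.09, a fall of 8% (88 to 81).
- As stated: 148/81 = 1.83, a fall of 45%.

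**4. The superseded 148.** At one-sided 0.01 and 80% power, Schoenfeld needs 127.0 (HR 0.57) to 130.7 (HR 0.5746) events, and Freedman 133.8 to 137.5. Dividing the HR 0.57 figures by 0.97 for the 3% loss gives about 132 and 138. Power with 148 events:
- HR 0.57: ½ × √148 × 0.562 − 2.326 = 1.093, so 86.3% (Freedman 84.3%).
- HR 0.5746: 85.2% (Freedman 83.2%).
- A 10,000-run log-rank simulation with exponential PFS and 260 patients gives about 85%.

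So 148 does not reproduce as 80% from the stated inputs. Two possible origins can be computed, and neither is documented:
- Two-sided 0.01 at HR 0.57 gives 147.8 events. However, every passage says one-sided, and a two-sided 0.04 would leave OS at about 70–71% at HR 0.70, not 78%.
- Expected events at month 45. Assume exponential PFS, 130 patients per arm, uniform 36-month enrolment and randomisation four months later, so follow-up runs from 5 to 41 months. This gives 85.4 + 62.1 = 147.5, so 148 fits the stated timing.

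**5. Does either slip reach the live rule?** SAP 1.4.2 and SAP 3 both give 81 events at one-sided 5%, and SAP 2.1 uses the same count. The transposed figures and 148 are not inputs to the current calculation, which uses only 0.05, 80% and the two medians.

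**The case for a change.** The best case for acting is that the transposition is a real contradiction inside the current SAP. It is more than a difference between old and new text, because the SAP misreports its own history at the place where a late change of endpoint is explained. Correcting it would take one bracket. All of that stands as a description. But the correct split appears in SAP 1.4.1, immediately before, and three times in the protocol, so an attentive reader is not misled for long. No analysis step uses the bracket.

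The case on 148 is weaker. Protocol 18.3 names EAST and 10,000-run simulations under a piecewise exponential model that drops events before randomisation, but it does not give the hazard pieces. A plain exponential check is therefore not the same calculation, although under proportional hazards the difference should be small. The scenarios also do not settle the matter. The protocol says "The alternative hypothesis of treatment benefit corresponds to an HR for PFS equal to 0.55, 0.60 and 0.65 and an OS HR of 0.7" and that "Power of 78% for testing OS from randomisation to end of trial and of 80% for testing PFS were generally aimed and achieved", but not that each scenario was held at 148 events.

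Its reported results are internally consistent with about 80%. Joint rejection of 67–68% divided by conditional rejection of 85–87% gives PFS power between 0.67/0.87 = 77% and 0.68/0.85 = 80%. With OS at 78%, PFS at 80% gives at least one rejection of 0.80 + 0.78 − 0.67 or 0.68, which is 90–91% and inside the stated 88–91%. PFS at 85% would give about 95–96%. These results are for hazard ratios of 0.55 to 0.65, so they do not explain 148 at 0.57. They do make the gap an unexplained difference, and not a demonstrated power error.

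**Conclusion.** No change to the plan follows. The bracket in SAP 1.4.2 is a clerical slip: the previous one-sided split was 0.01 for PFS and 0.04 for OS, and the PFS alpha rose from 0.01 to 0.05 when OS ceased to be co-primary, with the overall one-sided level unchanged at 0.05. The 148-event figure cannot be reproduced as 80% power from its stated inputs. It carries roughly 83–86%, or about 17–21 events more than Schoenfeld requires (148 − 130.7 to 148 − 127.0). That errs on the safe side, and the design it belonged to has been abandoned.

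The rule that will decide the trial is stated consistently and checks out at 80.5 events. These figures assume proportional hazards, 1:1 allocation and the documents' medians. The one unknown, the software and simulation settings behind 148, cannot affect the current test. A corrected bracket or a footnote on superseded power would tidy the record but would not change the alpha, the event count, the analysis or what the trial can conclude.
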